6.7. ADDITIONAL ANALYSIS

6.7.1.SF-36 Total Physical Score Comparison

Evaluation	Level of	Analysis Blan			
Variable / Question	Measurement	Analysis Flan			
All Assessments – SF-36 Tota	al Physical Score	e Comparison			
Use "SF-36 Total Physical Score Pre-On Ipoints]" and "SF-36 Total Physical Score 3 Months Ipoints]":					
Based on the underlying distribution of the data in both groups and the result of the normality assessment, either					
the parametric paired samples t-test or the non-parametric Wilcoxon test will be used to compare "SF-36 Total					
Physical Score Pre-Op [points]" and	"SF-36 Total Physic	cal Score 3 Months [points]" to evaluate the SF-36			
PCS score change by subject (improvement or decrease).					
The complete available SPSS tables c	ontent related to eith	er the paired samples t-test or the Wilcoxon test will			
be included in the final report.					
(Variable(s): VISITDT; PCSSCORE)					
Use "SF-36 Total Physical Score Pro	e-Op [points]" and ".	SF-36 Total Physical Score 6 Months [points]":			
Based on the underlying distribution of	of the data in both gro	oups and the result of the normality assessment, either			
the parametric paired samples t-test of	r the non-parametric	Wilcoxon test will be used to compare "SF-36 Total			
Physical Score Pre-Op [points]" and	"SF-36 Total Physic	cal Score 6 Months [points]" to evaluate the SF-36			
PCS score change by subject (improv	ement or decrease).				
The complete available SPSS tables c	ontent related to eith	er the paired samples t-test or the Wilcoxon test will			
be included in the final report.					
(Variable(s): VISITDT; PCSSCORE))				
Use "SF-36 Total Physical Score Pro	e-Op [points]" and "	SF-36 Total Physical Score 12 Months [points]":			
Based on the underlying distribution of	of the data in both gro	bups and the result of the normality assessment, either			
the parametric paired samples t-test of	r the non-parametric	Wilcoxon test will be used to compare "SF-36 Total			
Physical Score Pre-Op [points]" and	"SF-36 Total Physic	cal Score 12 Months [points]" to evaluate the SF-36			
PCS score change by subject (improv	ement or decrease).	an the named complex t test on the Wilcower test will			
he included in the final report	ontent related to entit	er me paried samples t-test of me wheoxon test will			
(Variable(s): VISITDT: PCSSCOPE)					
Use "SE 36 Total Physical Score 3	 Months Ingints]" and	"SE 36 Total Physical Score 6 Months Incints".			
Based on the underlying distribution (of the data in both gro	uns and the result of the normality assessment either			
the parametric paired samples t-test of	r the non-narametric	Wilcoxon test will be used to compare "SF-36 Total			
Physical Score 3 Months [points]" a	nd "SF-36 Total Phy	vical Score 6 Months Inoints I" to evaluate the SF-36			
PCS score change by subject (improv	ement or decrease).				
The complete available SPSS tables c	ontent related to eith	er the paired samples t-test or the Wilcoxon test will			
be included in the final report.					
(Variable(s): VISITDT; PCSSCORE))				
Use "SF-36 Total Physical Score 3 M	Months [points]" and	"SF-36 Total Physical Score 12 Months [points]":			
Based on the underlying distribution of	of the data in both gro	oups and the result of the normality assessment, either			
the parametric paired samples t-test of	the parametric paired samples t-test or the non-parametric Wilcoxon test will be used to compare "SF-36 Total				
Physical Score 3 Months [points]" and "SF-36 Total Physical Score 12 Months [points]": to evaluate the SF-					
36 PCS score change by subject (imp	36 PCS score change by subject (improvement or decrease).				
The complete available SPSS tables c	ontent related to eith	er the paired samples t-test or the Wilcoxon test will			
be included in the final report.		-			
(Variable(s): VISITDT; PCSSCORE)					
Use "SF-36 Total Physical Score 6 M	Months [points]" and	"SF-36 Total Physical Score 12 Months [points]":			
Based on the underlying distribution of	of the data in both gro	pups and the result of the normality assessment, either			
the parametric paired samples t-test or the non-parametric Wilcoxon test will be used to compare "SF-36 Total					

Physical Score 6 Months [points]" and "SF-36 Total Physical Score 12 Months [points]": to evaluate the SF-36 PCS score change by subject (improvement or decrease). The complete available SPSS tables content related to either the paired samples t-test or the Wilcoxon test will be included in the final report. (Variable(s): VISITDT; PCSSCORE)

Table 6.7.1: All Assessments - SF-36 Total Physical Score Comparison Tables List

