3.1. FRAMEWORK

All quantitative variables, including those based on calculations (secondary elements), will be analyzed with a case summary evaluation before the detailed characteristics and parameter can be evaluated. A case summary contains a listing of the number of valid cases/values, missing cases/values (if any) and total cases/values in the specific analysis. In general, as central position parameter for quantitative

variables the mean and median will be analyzed. As variation parameter the standard deviation, 95% confidence interval of the mean, interquartile range and maximum and minimum will be calculated. All quantitative variables will be assessed for normality used the Shapiro-Wilk test. For optional visualization of quantitative variables, box-and-whisker plots will be used. Additional analyses like skewness and kurtosis measures of standard errors are also optional.

All qualitative variables, including those based on summaries (secondary elements), will be analyzed listing the proportions, frequencies, column and row totals and missing proportion (if any).

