4.10. ASSUMTIONS

In case of deviation from assumptions (e.g. normality), non-parametric methods will be used for analysis. No transformation of such data will be performed.

5. Population and Progress

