6.7.6. SF-36 Total Physical Score – Within subject changes by visit

The within subject score changes of the SF-36 Total Physical Score from visit to visit will be analyzed to help identifying the changes on the subject level. This analysis is part of the report.

Evaluation Variable / Question	Level of Measurement	Coding and Analysis Plan			
All Assessments - SF-36 Total Physical Score Within Subject Changes					
Creation of variable "SF-36 Total Physical Score change between pre-operative visit and 3 Months [points]"	Quantitative, interval	Calculate difference (could be negative or positive).			

Difference between "SF-36 Total Physical Score Pre-Op [points]" with "SF-36 Total Physical Score 3 Months [points]" (Variable(s): VISITDT; PCSSCORE)		Case summary with number and percentage of valid cases/values, missing cases/values (if any) and total cases/values. Mean, median, interquartile range, maximum, minimum, standard deviation, 95% confidence interval for mean, Shapiro- Wilk Test.
Creation of variable "SF-36 Total Physical Score change between pre-operative visit and 6 Months [points]" Difference between "SF-36 Total Physical Score Pre-Op [points]" with "SF-36 Total Physical Score 6 Months [points]" (Variable(s): VISITDT; PCSSCORE)	Quantitative, interval	Calculate difference (could be negative or positive). Case summary with number and percentage of valid cases/values, missing cases/values (if any) and total cases/values. Mean, median, interquartile range, maximum, minimum, standard deviation, 95% confidence interval for mean, Shapiro- Wilk Test.
Creation of variable "SF-36 Total Physical Score change between pre-operative visit and 12 Months [points]" Difference between "SF-36 Total Physical Score Pre-Op [points]" with "SF-36 Total Physical Score 12 Months [points]" (Variable(s): VISITDT; PCSSCORE)	Quantitative, interval	Calculate difference (could be negative or positive). Case summary with number and percentage of valid cases/values, missing cases/values (if any) and total cases/values. Mean, median, interquartile range, maximum, minimum, standard deviation, 95% confidence interval for mean, Shapiro- Wilk Test.

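### SAP 6.7.1 chooses the paired PCS test from the distributions at the two visits, but the relevant condition is on the within-subject differences, which Table 6.7.6 already tests

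*SAP*

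**What the plan says.** SAP 6.7.1 lists six pairwise PCS comparisons among the pre-operative, 3-, 6- and 12-month assessments. In each row "the parametric paired samples t-test or the non-parametric Wilcoxon test will be used to compare" the two visits, and the choice rests on the "underlying distribution of the data in both groups and the result of the normality assessment". The stated aim is to evaluate the "PCS score change by subject (improvement or decrease").

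SAP 6.7.6 builds a change variable for each of the same six pairs, for example "SF-36 Total Physical Score change between pre-operative visit and 3 Months [points]", with the instruction "Calculate difference (could be negative or positive)". For each it plans "Mean, median, interquartile range, maximum, minimum, standard deviation, 95% confidence interval for mean, Shapiro- Wilk Test".

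Two general statements also apply. SAP 3.1 says "All quantitative variables will be assessed for normality used the Shapiro-Wilk test", and SAP 4.10 says "In case of deviation from assumptions (e.g. normality), non-parametric methods will be used for analysis".

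**The concern.** A paired t-test is a one-sample t-test on the within-subject differences. Its normality condition applies to those differences and not to the scores at either visit. SAP 6.7.1 directs the analyst to the two visit distributions and never names the difference. Table 6.7.6 runs the relevant check, but its result does not feed into the choice.

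The final report could therefore show a change variable that passes Shapiro-Wilk, summarised by a mean change and 95% CI, beside a Wilcoxon p-value chosen because the scores at one visit were skewed. The rule also does not say how two visit-level results combine when one passes and the other fails, so two analysts could run different tests on the same data.

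**Working it through.** **Nearest stated figure.** The documents give no figure for how the selection rule behaves. The design figure used here is the evaluable sample size in SAP 3.2: 61 subjects, difference 43.48 − 39.25 = 4.23, SD 13.04, one-sided alpha 0.05. The noncentrality is 4.23/13.04 × √61 = 2.53. The noncentral t gives power 0.805 at n = 61 and 0.799 at n = 60, so the stated 61 and 0.805 reproduce. The check uses 61 pairs.

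**Why the visit distributions can mislead.** The test statistic is mean(D)/(SD(D)/√n), with D = Y2 − Y1. Suppose Yj = S + ej, where S is a skewed subject effect common to both visits and ej is normal visit error. Then D = e2 − e1: the skew cancels and D is exactly normal, although both visits are skewed.

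**Normal scores.** Requiring two Shapiro-Wilk tests at 5% to pass gives a switching rate near 1 − 0.95² = 0.0975 if the two tests were independent. One test on D gives about 0.05.

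**Simulation.** There were 1,500 data sets per scenario, 61 pairs, SD 13.04. Visit rule: keep the t-test only if Shapiro-Wilk p > 0.05 at both visits. Difference rule: keep it if p > 0.05 on D. Correlation (r) and skew (gamma shape; smaller is more skewed) are assumptions, because the documents give neither. The differences are truly normal in every row.

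| Assumed scores | Visit rule leaves t-test | Difference rule leaves t-test | Rules choose different tests |
|---|---|---|---|
| Bivariate normal, r 0.3 | 10.8% | 4.5% | 14.4% |
| Bivariate normal, r 0.7 | 9.8% | 5.1% | 14.6% |
| Shared skew, shape 8, r 0.5 | 19.5% | 4.6% | 22.4% |
| Shared skew, shape 4, r 0.7 | 48.9% | 5.0% | 48.3% |
| Shared skew, shape 2, r 0.7 | 73.8% | 4.3% | 71.7% |

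A separate set at n = 61 gave 8-11% for bivariate normal scores. With subject SD 9 and error SD 5 (correlation 81/(81 + 25) = 0.76), the visit rule left the t-test in 57-79% of data sets for shapes 4 to 2.

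**Effect on conclusions, normal differences** (two-sided 5% assumed; r 0.5, bivariate normal, 1,000 data sets). With no change, the t-test rejects in 5.7% and Wilcoxon in 6.2%, and they agree in 98.1%. With a 4.23-point change, power is 0.687 against 0.676 and they agree in 93.5%. Carried through the two rules, the significance decision was the same in about 94-99.8% of data sets, so it differs in about 0-6%.

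**Differences that are not normal.** If only the follow-up scores are skewed (shape 2), the visit rule keeps the t-test in 12% of data sets at r 0.3, against 55% for the difference rule. At r 0.7 the order reverses: 71% against 22%. In the asymmetric cases run, the two tests agreed in 86-97% at changes of 0 to 4.23 points, so the 0-6% figure should not be carried over to them. With shape 2, r 0.5 and zero mean change, the t-test rejected in 5.0% and Wilcoxon in 8.5%.

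**The case against.** The wording can be read more kindly. The rule has a second limb, the normality assessment, which names no variable. SAP 3.1 applies Shapiro-Wilk to every quantitative variable, calculated ones included, and SAP 4.10 switches on departure from assumptions, which for a paired t-test means the differences. This shows that the differences are omitted rather than expressly ruled out. It does not cure the problem, because 6.7.1 is the specific instruction and it names the data in both groups.

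A reader might infer that the rule often picks the wrong test. That is not supported:

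- The frequency cannot be derived from the documents. SAP 3.2 remarks that summary scores tend to deviate from normality, which makes skew plausible but does not quantify it.
- The high percentages count changes of test, not errors. Wilcoxon is valid for symmetric differences and loses little power there.
- The visit rule is not uniformly worse at steering away from the t-test when the differences are skewed, as the r 0.3 follow-up case shows.

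A reader might also infer that the rule causes false positives by applying the t-test to skewed differences. It can select the t-test there, but in the skewed cases run at 61 pairs the t-test rejected in about 5% at zero mean change.

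It also stands that 6.7.1 is an additional analysis and that Table 6.7.6 reports mean changes with 95% CIs whichever test is run.

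**Conclusion.** The point holds as a mis-specified selection condition of low consequence. The rule in all six rows looks at the visit distributions, the condition that matters is on the differences, and the SAP already runs that check without using it.

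With truly normal differences at 61 pairs, the rule leaves the t-test in about 8-11% of data sets (bivariate normal scores) and up to about 80% (strong shared skew), against about 5% when selecting on the differences. The width of that range comes from the assumed skew and correlation, and from reading the rule as requiring normality at both visits. The resulting difference in significance decisions is about 0-6%. The primary one-sample comparison with 39.25 is unaffected. This is a worthwhile tidy-up rather than a threat to the trial's conclusions.

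**What to change.** Either change settles it:

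1. In all six rows of Table 6.7.1, replace the reference to the data in both groups with the distribution of the within-subject differences in Table 6.7.6. This is one phrase repeated six times, and the Shapiro-Wilk test it needs is already planned.
2. Pre-specify the paired t-test for all six comparisons, with Wilcoxon as a sensitivity analysis. This matches the mean changes and 95% CIs in Table 6.7.6. It would need a stated exception to the general switch in SAP 4.10.

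Neither needs new data or variables. The first has a small downside: it keeps a data-driven pre-test, and when the differences fail Shapiro-Wilk the Wilcoxon p-value will still differ in kind from the mean and CI in Table 6.7.6. The second avoids both.

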6.7.2. Weight-bearing status

As listed above, the weight bearing status will be evaluated and analyzed at the preoperative visit and at 3 months, 6 months and 12 months. The within subject changes from visit to visit will be analyzed in addition. This analysis is part of the final report.

The variable capturing weight bearing will be used with "yes" (including partial and full) versus "no" weightbearing.

Evaluation	Level of	Recoding
Variable / Question	Measurement	Recouning
All Assessments - Weight-b	earing status	
Recode initial weightbearing status at pre-op visit into new variable " Pre- Op Weightbearing Dichotomous " (Variable(s): VISITDT; WEIGHTBEAR)	Qualitative, nominal	The initial variable capturing weight bearing pre- op will be recoded with "yes" (including partial and full) versus "no" weightbearing.
Recode initial weightbearing status at pre-op visit into new variable "3 Months Weightbearing Dichotomous" (Variable(s): VISITDT; WEIGHTBEAR)	Qualitative, nominal	The initial variable capturing weight bearing at 3 months will be recoded with "yes" (including partial and full) versus "no" weightbearing.
Recode initial weightbearing status at pre-op visit into new variable "6 Months Weightbearing Dichotomous" (Variable(s): VISITDT; WEIGHTBEAR)	Qualitative, nominal	The initial variable capturing weight bearing at 6 months will be recoded with "yes" (including partial and full) versus "no" weightbearing.
Recode initial weightbearing status at pre-op visit into new variable "12 Months Weightbearing Dichotomous" (Variable(s): VISITDT; WEIGHTBEAR)	Qualitative, nominal	The initial variable capturing weight bearing at 12 months will be recoded with "yes" (including partial and full) versus "no" weightbearing.

Table 6.7.2.1: All Assessments – Weight-bearing status Recoding

New variables (10) will then be created for each possible pair/comparison. Negative changes (from "yes" to "no") will be coded with "negative change" and positive changes (from "no" to "yes") with be coded with "positive change". If there is no change (from "yes" to "yes" or from "no" to "no"), the coding will be "no change".

Evaluation Variable / Question	Level of Measurement	Coding and Analysis Plan
All Assessments - Weight-bearing statu	15	
Create new variable "Weightbearing status change between pre-operative visit and 3 months" based on comparison of "Pre-Op Weightbearing Dichotomous" with "3 Months Weightbearing Dichotomous" (Variable(s): VISITDT; WEIGHTBEAR)	Qualitative, nominal	 Negative changes (from "yes" to "no") = "negative change" Positive changes (from "no" to "yes") = "positive change" No change (from "yes" to "yes" or from "no" to "no") = "no change" Proportions, frequencies, column and row totals, missing proportion (if any).

Create new variable "Weightbearing status change between pre-operative visit and 6 months" based on comparison of "Pre-Op Weightbearing Dichotomous" with "6 Months Weightbearing Dichotomous" (Variable(s): VISITDT; WEIGHTBEAR)	Qualitative, nominal	 Negative changes (from "yes" to "no") = "negative change" Positive changes (from "no" to "yes") = "positive change" No change (from "yes" to "yes" or from "no" to "no") = "no change" Proportions, frequencies, column and row totals, missing proportion (if any). 		
Create new variable "Weightbearing status change between pre-operative visit and 12 months" based on comparison of "Pre-Op Weightbearing Dichotomous" with "12 Months Weightbearing Dichotomous" (Variable(s): VISITDT; WEIGHTBEAR)	Qualitative, nominal	 Negative changes (from "yes" to "no") = "negative change" Positive changes (from "no" to "yes") = "positive change" No change (from "yes" to "yes" or from "no" to "no") = "no change" Proportions, frequencies, column and row totals, missing proportion (if or w) 		
Create new variable "Weightbearing status change between 3 months and 6 months" based on comparison of "3 Months Weightbearing Dichotomous" with "6 Months Weightbearing Dichotomous" (Variable(s): VISITDT: WEIGHTBEAR)	Qualitative, nominal	 Negative changes (from "yes" to "no") = "negative change" Positive changes (from "no" to "yes") = "positive change" No change (from "yes" to "yes" or from "no" to "no") = "no change" Proportions, frequencies, column and 		
Create new variable "Weightbearing status change between 3 months and 12 months" based on comparison of "3 Months Weightbearing Dichotomous" with "12 Months Weightbearing Dichotomous" (Variable(s): VISITDT; WEIGHTBEAR)	Qualitative, nominal	 row totals, missing proportion (if any). Negative changes (from "yes" to "no") = "negative change" Positive changes (from "no" to "yes") = "positive change" No change (from "yes" to "yes" or from "no" to "no") = "no change" Proportions, frequencies, column and row totals, missing proportion (if any). 		
Create new variable "Weightbearing status change between 6 months and 12 months" based on comparison of "6 Months Weightbearing Dichotomous" with "12 Months Weightbearing Dichotomous" (Variable(s): VISITDT; WEIGHTBEAR)	Qualitative, nominal	 Negative changes (from "yes" to "no") = "negative change" Positive changes (from "no" to "yes") = "positive change" No change (from "yes" to "yes" or from "no" to "no") = "no change" Proportions, frequencies, column and row totals, missing proportion (if any). 		

Table 6.7.2.2: All Assessments - Weight-bearing status Tables List

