Creation of variable Number of previous history of surgery to the Contralateral Tibia by Subject (Variable(s): CONTRPROCNM1; CONTRPROCNM2; CONTRPROCNM3; CONTRPROCNM4)	Qualitative, nominal	Proportions, frequencies, column and row totals, missing proportion (if any).		x	
Weight Bearing (Variable(s): WEIGTBEAR)	Qualitative, nominal	Proportions, frequencies, column and row totals, missing proportion (if any).	X	X	
Weight Bearing Specification (Variable(s): WEIGTSPC)	Qualitative, nominal	Proportions, frequencies, column and row totals, missing proportion (if any).	X	X	
External Support Prior to the Tibia Fracture (Variable(s): EXTRSUPP)	Qualitative, nominal	Proportions, frequencies, column and row totals, missing proportion (if any).	X	Х	

Table 6.2.4: Pre-Operative Visit Form – Subject Evaluation Tables List

Evaluation Variable / Question	Level of Measurement	Analysis Plan	Inclusion		
Pre-Operative Visit Form – SF-36 Score (post fracture, prior to					N/A
surgery)			ш	ΓN	
In general, would you say your	Oualitative.	Proportions, frequencies,			
health is (Variable(c): GH01 PESPONSE)	nominal	column and row totals,			X
Compared to one year ago, how		missing proportion (if any).			
would you rate your health in	Qualitative,	Proportions, frequencies,			37
general now?	nominal	column and row totals,			X
(Variable(s): HT_RESPONSE)		missing proportion (if any).			
Vigorous activities, such as running,		Proportions, frequencies,			
lifting neavy objects, participating in strenuous sports	Qualitative,	column and row totals,			Х
(Variable(s): PF01 RESPONSE)	nommar	missing proportion (if any).			
Moderate activities, such as moving a		Proportions fraguencies			
table, pushing a vacuum cleaner,	Qualitative,	column and row totals			x
bowling, or playing golf	nominal	missing proportion (if any).			
(Variable(s): PF02_RESPONSE)		Proportions fraguencies			
Lifting or carrying groceries	Qualitative,	column and row totals.			x
(Variable(s): PF03_RESPONSE)	nominal	missing proportion (if any).			
Climbing soveral flights of stairs	Qualitative	Proportions, frequencies,			
(Variable(s): PF04 RESPONSE)	nominal	column and row totals,			Х
	nominar	missing proportion (if any).			
Climbing one flight of stairs	Qualitative,	Proportions, frequencies,			v
(Variable(s): PF05_RESPONSE)	nominal	missing proportion (if any)			л
		Proportions, frequencies.			
Bending, kneeling, or stooping	Qualitative,	column and row totals,			Х

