6.5. POST-OPERATIVE CHARACTERISTICS

The analysis of the Postoperative data must be performed separately for each follow-up visit listed in table 4.4 in accordance to the following tables in this chapter. New Variables must be created individually for each follow-up visit.

Evaluation	Level of						
Variable / Ouestion	Measurement	Analysis Plan	I	nclusio	n		
Post-Operative Visit Form – Ph	ysical Exam		IR	FR	N/A		
Date of Visit:	Date/Time	None			Х		
Creation of variable Difference between Date of Surgery [dd.mm.yyyy] and Date of Visit [dd.mm.yyyy] In [days] (Variable(s): VISITID; VISNAME)	Case summary with number and percentage of valid cases/values, missing cases/values (if any) and total cases/values.Quantitative, ratioMean, median, interquartile range, maximum, minimum, standard deviation, 95% confidence interval for mean, Shapire Wilk Tast		Quantitative, ratio Quanti			х	
Is the subject weight bearing? (Variable(s): WEIGHTBEAR)	Qualitative, nominal	Proportions, frequencies, column and row totals, missing proportion (if any).	Х	Х			
Specify, Full or Partial (Variable(s): FULPART)	Qualitative, nominal	Proportions, frequencies, column and row totals, missing proportion (if any).	Х	Х			
Is the subject using an external support? (Variable(s): EXTRSUPP)	Qualitative, nominal	Proportions, frequencies, column and row totals, missing proportion (if any).	X	Х			
Has the bone consolidated (consider weight-bearing, pain and imaging)? (Variable(s): BONECONS; EXPLN)	Qualitative, nominal	Proportions, frequencies, column and row totals, missing proportion (if any). Listing of given explanations.	Х	Х			

Table 6.5.1: Post-Operative Visit Form – Physical Exam Tables List

Evaluation	Level of Massurament			clusion	
Post-Onerative Visit Form – SF	-36 Score		IR	FR	N/A
In general, would you say your health is (Variable(s): GH01 RESPONSE)	Qualitative, nominal	Proportions, frequencies, column and row totals, missing proportion (if any).			X
Compared to one year ago, how would you rate your health in general now? (Variable(s): HT RESPONSE)	Qualitative, nominalProportions, frequencies, column and row totals, missing proportion (if any).				х
Vigorous activities, such as running, lifting heavy objects, participating in strenuous sports (Variable(s): PF01_RESPONSE)	Qualitative, nominalProportions, frequencies, column and row totals, missing proportion (if any).				Х

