6.7.3. External Support

As listed above, the status of the subject using external support will be evaluated at the preoperative visit and at 3 months, 6 months and 12 months. The within subject changes from visit to visit will be analyzed in addition. This analysis is part of the final report.

The variable capturing "Is the subject using an external support" will be used and recoded into a new variable for each visit with the options "no" (using no support at all) versus "yes" (including Walker, Cane, One Crutch or Two Crutches).

Evaluation Variable / Question	Level of Measurement	Recoding
All Assessments – Extern	al support stati	18
Recode initial external support status at pre-op visit into new variable "Pre- Op External Support Dichotomous" (Variable(s): EXTRSUPP)	Qualitative, nominal	The variable capturing "Is the subject using an external support" will be used and recoded into a new variable for each visit with the options "no" (using no support at all) versus "yes" (including Walker, Cane, One Crutch or Two Crutches).
Recode initial external support status at pre-op visit into new variable "3	Qualitative, nominal	The variable capturing "Is the subject using an external support" will be used and recoded into a new variable for each visit with the options "no" (using no support at all)

Months External Support Dichotomous" (Variable(s): VISITDT; EXTRSUPP)		versus "yes" (including Walker, Cane, One Crutch or Two Crutches).
Recode initial external support status at pre-op visit into new variable "6 Months External Support Dichotomous" (Variable(s): VISITDT; EXTRSUPP)	Qualitative, nominal	The variable capturing "Is the subject using an external support" will be used and recoded into a new variable for each visit with the options "no" (using no support at all) versus "yes" (including Walker, Cane, One Crutch or Two Crutches).
Recode initial external support status at pre-op visit into new variable "12 Months External Support Dichotomous" (Variable(s): VISITDT; EXTRSUPP)	Qualitative, nominal	The variable capturing "Is the subject using an external support" will be used and recoded into a new variable for each visit with the options "no" (using no support at all) versus "yes" (including Walker, Cane, One Crutch or Two Crutches).

Table 6.7.3.1: All Assessments – External Support Recoding

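### The weight-bearing and external-support change tables code movement between partial and full, or between support types, as no change, and the support baseline is mislabelled

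*SAP*

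**What the plan says.** SAP 6.7.2 reduces weight-bearing at each visit to two levels: "The variable capturing weight bearing will be used with 'yes' (including partial and full) versus 'no' weightbearing". The change rule follows: "If there is no change (from 'yes' to 'yes' or from 'no' to 'no'), the coding will be 'no change". Each of the six rows in Table 6.7.2.2 is built from the two-level variables; the first, for example, is "based on comparison of 'Pre-Op Weightbearing Dichotomous' with '3 Months Weightbearing Dichotomous".

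SAP 6.7.3 does the same for external support. Subjects without any support are coded no, and all others "yes' (including Walker, Cane, One Crutch or Two Crutches". A yes-to-yes pair is again coded as no change.

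The finer weight-bearing detail is collected. Table 6.2.4 has "Weight Bearing Specification (Variable(s): WEIGTSPC" before surgery, and Table 6.5.1 has "Specify, Full or Partial (Variable(s): FULPART" at follow-up. Both are tabulated as frequencies for the interim and final reports. Neither variable is named in 6.7.2, which lists only the visit date and the yes/no item.

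The two support items ask different things. The baseline item in Table 6.2.4 is "External Support Prior to the Tibia Fracture". The follow-up item in Table 6.5.1 is "Is the subject using an external support? (Variable(s): EXTRSUPP". Table 6.7.3.2 nevertheless labels its three baseline comparisons as change from the pre-operative visit.

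**The concern.** The SAP promises an analysis of how each subject changes between visits, and these two sets of tables are where it delivers that for weight-bearing and support. Merging the categories before coding change removes part of the movement the tables are meant to describe. For a subject already bearing some weight, the only change that the weight-bearing rows can register is a return to none. A subject who goes from partial to full, and one who goes from full to partial, fall in the same unchanged category.

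The baseline label raises a different problem. A subject who used no support before the injury and none at 12 months has returned to pre-injury status. The row reports this as no change since the pre-operative visit, which a reader would take as a comparison with the injured state just before surgery.

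At stake is the accuracy of two descriptive sections of the final report, not the trial's main conclusion.

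**Working it through.** The plan states no figure here to reproduce, so the check applies its coding rule to every ordered pair of different states.

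**Inputs**

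- Weight-bearing states: none, partial, full (SAP 6.7.2 and Table 6.5.1). The response options of the pre-operative specification item are not printed; I assume they match, since 6.7.2 describes the pre-operative variable as including partial and full.
- Support states: none, walker, cane, one crutch, two crutches (SAP 6.7.3).
- Rule: every state except none is recoded yes, and yes-to-yes is coded no change.

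**Counts**

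With k states there are k(k − 1) real transitions. The k − 1 merged states have (k − 1)(k − 2) transitions among themselves, all coded no change.

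- Weight-bearing, k = 3: 3 × 2 = 6 transitions, of which 2 × 1 = 2 are coded no change (partial to full, full to partial).
- External support, k = 5: 5 × 4 = 20 transitions, of which 4 × 3 = 12 are coded no change (every move among walker, cane, one crutch and two crutches).

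These are counts of possible transitions. The documents give no distribution of states, so they cannot be turned into a proportion of subjects.

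**Whether the per-visit tables recover the loss**

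Take subjects bearing weight at both of two visits. Let a be the number who move from partial to full and b the number who move from full to partial. The per-visit frequencies of full weight-bearing among them differ by a − b. The change table counts all a + b of them as unchanged. So the reader can learn at most the net difference, not a or b. Even the net difference requires the same subjects at both visits. That may not hold: the schedule of events lets the consolidation assessment lapse once consolidation is seen and moves the SF-36 to telephone, and weight-bearing and support are recorded on the same physical-exam form as consolidation. Whether they then go unrecorded is not stated.

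**Direction of the support coding**

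| Place in SAP 6.7.3 | No support to support | Support to no support |
|---|---|---|
| Text before Table 6.7.3.2 | negative | positive |
| All six rows of Table 6.7.3.2 | positive | negative |

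The two are opposite for every result other than no change. The table rows use the same yes/no coding as the weight-bearing table, where yes has the reverse meaning.

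**The case against.** The strongest reply is that little is lost. Full versus partial and external support are tabulated at every follow-up visit for both report types, and at baseline, so a shift in the group from partial to full would be visible. The dichotomy is explicit and pre-specified. The analyses are additional and descriptive, with no test or threshold. Subject-level physical change is also analysed on the SF-36 PCS for all six visit pairs (SAP 6.7.1 and 6.7.6). All of this is correct and limits the weight of the point. It does not restore the pairing within subjects for these two measures.

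A reader might infer more than the documents support:

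- *The tables will show mostly no change.* Nothing in the documents gives the frequency of each state. Three of the six weight-bearing rows start before surgery, where a move from none to any weight-bearing is coded positive, and stopping all support also registers as a change.
- *Failed healing will be hidden.* Reading full-to-partial as a sign of failed healing is clinical inference from outside the documents. Consolidation has its own secondary endpoint at 3, 6 and 12 months, and reasons for reoperation are tabulated.
- *Twelve of 20 support transitions are missed improvement or worsening.* The SAP treats support as nominal and gives no order for walker, cane and crutches. The 12 are unreported movements without a stated direction.

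**Conclusion.** The point holds, at minor severity. In 6.7.2 and 6.7.3, movement between partial and full weight-bearing and between support types is reported as no change (2 of 6 and 12 of 20 possible transitions). The per-visit tables preserve only the margins. The baseline support rows compare with pre-fracture status under a pre-operative label. These conclusions rest on the coding rules as written, on the assumption that the pre-operative specification item records full or partial, and on the support item holding the types that 6.7.3 names. How many subjects would be affected cannot be derived.

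The effect stops at descriptive additional analyses. The one-sample test of 12-month PCS against 39.25 and the sample size do not depend on either variable.

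**What to change.** 1. In SAP 6.7.2, code change on none < partial < full, using WEIGTSPC before surgery and FULPART at follow-up together with the yes/no item. Report improved, unchanged and worsened, with a cross-table for each pair of visits. Keep the yes/no version as a supplement.
2. In SAP 6.7.3, add a within-subject cross-table of the ungrouped support categories. Do not impose a ranking of support types that the documents do not give.
3. Relabel the three external-support baseline comparisons (3, 6 and 12 months) as change from pre-fracture status.
4. In the same edit, reconcile the direction coding in 6.7.3 so that the text and the six rows agree. Also correct the announced number of new variables in both sections: each says 10, but four time points give 4 × 3 / 2 = 6 pairs, and six are listed.

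No new data are needed. The cost is SAP wording, a little more recoding, and cross-tables that will be sparse with about 80 subjects.
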